10.2 STATISTICAL HYPOTHESES

Aim 1: To demonstrate the effectiveness of a SSU AHF management strategy vs. usual AHF care (i.e. inpatient admission), using a randomized, controlled, simple trial design.

- **Hypothesis 1a:** SSU treated patients will have one more DAOOH within 30 days post-randomization vs. usual care arm. Assuming a 10% attrition rate, we will randomize 534 patients 1:1, which will provide 80% power (alpha 0.05, two-sided) to demonstrate a one-day difference in the primary outcome at 30 days post-randomization.
- **Hypothesis 1b:** An AHF SSU strategy of care will lead to significant improvement in QoL scores at 30 days post-discharge compared with usual care. QoL will be assessed with the KCCQ.⁵⁹

Aim 2: To demonstrate if a SSU AHF strategy of care leads to equivalent or improved adherence to HF guidelines at time of discharge compared to usual care.

- **Hypothesis 2:** Adherence to HF guidelines at time of discharge in the SSU arm is equivalent or better than adherence in the usual care arm.

10.3 ANALYSIS DATASETS

The Full Analysis Set (FAS) will include all randomized patients. In accordance with the intent-to-treat principle, patients will be analyzed by the group to which they were randomized. Misrandomized patients (patients randomized in error

who did not receive any study intervention) will be excluded. Analyses in the FAS will constitute the main efficacy results for the primary and secondary study efficacy endpoints.

The Per Protocol Set (PPS) will be a subset of the FAS and will exclude patients with major protocol violations. The major protocol violations that will result in exclusion from the PPS will be identified. Patients will be analyzed in the treatment group to which they were randomized. Results of analyses in this analysis population will support the primary efficacy analyses in the FAS.

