5.4.2 HANDLING OF PARTICIPANT WITHDRAWALS OR TERMINATION

The Full Analysis Set (FAS) will include all randomized patients. In accordance with the intent-to-treat principle, patients will be analyzed by the group to which they were randomized. Misrandomized patients (patients randomized in error who did not receive any study intervention) will be excluded. Analyses in the FAS will constitute the main efficacy results for the primary and secondary study efficacy endpoints.

The Per Protocol Set (PPS) will be a subset of the FAS and will exclude patients with major protocol violations. The major protocol violations that will result in exclusion from the PPS will be identified. Patients will be analyzed in the treatment group to which they were randomized. Results of analyses in this analysis population will support the primary efficacy analyses in the FAS.

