6.1.1 TREATMENT PROTOCOL

The algorithm below outlines the SSU AHF protocol.

Arm 1. SSU AHF Strategy: 'Short stay' is defined as < 24 hours. All SSU are monitored beds. Nursing ratios are similar to telemetry wards. Four principles of SSU AHF management are outlined: 1) relief of HF symptoms and signs; 2) decongestion while observing and correcting any electrolyte imbalances; 3) hemodynamic improvement; and 4) robust care transitions with an emphasis on guideline directed medication reconciliation and guideline recommended therapy at discharge.^{16,46} One potential advantage of the SSU AHF strategy is protocol driven care. (See Figure 3, next page) This figure is adapted from the ESC and SCPC Guidelines, primarily adding greater detail regarding vasodilator and diuretic dosing.⁴⁷ "Warm and wet" defines the HF phenotype from the Nohria et.al. classification: well perfused, volume overloaded.⁴⁸ The discharge criteria are taken from the SCPC guidelines on observation unit care.¹⁶

Arm 2. Usual care (defined by inpatient admission for AHF) was chosen as the comparator. In 2009, Dawson et.al. published the background framework for the 2005 NIH funded meeting on "Considering Usual Care in Clinical Trial Design: Scientific and Ethical Issues."⁴⁹ These principles informed our decision to use 'usual care' as the comparator.

One specific principle: consideration of ‘usual care’ when a comparator hypothesizes to be better than or equivalent to current clinical practice.⁴⁹ Hospitalization is the dominant strategy of care for over 80% of patients who present to the ED with AHF; thus, it provides the best real-world comparison of AHF care.⁵⁰ The median length of stay is 4.3 days.¹ We expect nearly all usual care patients to be cared for on general wards or telemetry and not ICU level of care, given our lower risk eligibility criteria. Guidelines are clear on suggested best practices for management.⁴⁹ Admittedly, the evidence supporting these statements in AHF are not as robust as chronic HF. This is one reason usual care has frequently been used in AHF therapeutic clinical trials.⁵¹⁻⁵³ Nevertheless, we will encourage guideline adherence in BOTH arms of the trial, both during hospitalization and pre-discharge. As hospitals are penalized on excessive 30-day readmissions, each participating hospital has a transitional care plan. In keeping with the pragmatic study design, each study arm will utilize their existing transitional care programs.

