10.1.1 ENDPOINTS AND RATIONALE

To ensure patient-centered endpoints, we twice met with patients and caregivers through two community engagement studios.⁵⁴ Patients prefer to be healthy and have a good QoL. If a safe alternative is available, patients prefer not to be hospitalized.

The **primary outcome** is **days alive and out of hospital (DAOOH) at 30 days post-randomization**. Unlike time-to-event analyses that ignores repeat events and gives equal weight to components of a composite endpoint,⁵⁵ DAOOH accounts for both frequency and duration of hospitalization and also weights mortality most heavily.^{55,56} This endpoint has also been suggested as a quality metric rather than re-hospitalization alone.⁵⁷

The **two secondary outcomes** are 1) **QoL using the KCCQ**. Patients desire not only to live longer, but to live better; or at minimum, not be worse after an acute health care related event.⁵⁸ Patients with advanced HF would trade survival time (or days alive) for a better QoL.⁵⁸ Our pilot work supports the feasibility of assessing QoL in the acute setting and suggests changes in scores are related to hospital re-visits.⁵⁹ We hypothesize that fewer days in the hospital in our SSU arm will also lead to a greater QoL. Interviews of hospitalized AHF patients suggest **they would prefer a shorter hospital stay or avoid an admission altogether**, assuming safety and outcomes are similar or better than hospitalization. Thus, assessing QoL is a key aim.

The KCCQ is a patient-reported, validated survey instrument designed to measure QoL in chronic HF patients.⁶⁰ Lower scores equal lower patient-reported QoL. **KCCQ scores predict adverse outcomes – namely hospitalization and mortality.** Importantly, the KCCQ demonstrates responsiveness to clinical change.⁶⁰⁻⁶²

A change of five points has been previously shown to be clinically significant, and will be assessed prior to discharge and day 30 post-randomization.⁶²

2) Cost effectiveness analysis, described in detail below.

NOTE: For patients randomized to SSU who worsen PRIOR to going to SSU, this will be counted the same as a hospitalization from the SSU.

ADDITIONAL ENDPOINTS

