10.6 MEASURES TO MINIMIZE BIAS

10.6.1 ENROLLMENT/ RANDOMIZATION/ MASKING PROCEDURES

Patients will be randomized 1:1 to one of the two study arms, but stratified by site to ensure equal site representation. A central computer generated randomization scheme with random block sizes of two, four, and six will be created, stratified by site. The REDCap randomization module will be utilized to generate the randomization schema and patient allocation.

Due the nature of the intervention and the clinical setting, this is an unblinded trial.

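### The Full Analysis Set drops misrandomized patients by an undefined test of care received after an unblinded allocation, so the exclusion can act unequally between the arms

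*Combined protocol and SAP*

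**What the plan says.** Section 10.3 opens with "The Full Analysis Set (FAS) will include all randomized patients" and invokes intention to treat, with patients analysed in their assigned group. Section 5.4.2 carries the same text. Both then make an exception, which in 10.3 begins "Misrandomized patients (patients randomized in error" and in 5.4.2 reads in full: "Misrandomized patients (patients randomized in error who did not receive any study intervention) will be excluded". The set matters because "Analyses in the FAS will constitute the main efficacy results for the primary and secondary study efficacy endpoints".

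Five other places bear on how the exception would work:

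- Section 6.1.1 on the control arm: "Usual care (defined by inpatient admission for AHF) was chosen as the comparator".
- Section 10.4.3.1, on mortality and rehospitalization, refers to both arms as intervention arms.
- Section 10.6.1 on masking: "this is an unblinded trial".
- Section 10.1.1, in a note: "For patients randomized to SSU who worsen PRIOR to going to SSU, this will be counted the same as a hospitalization from the SSU".
- Section 5.3 labels as screen failures those patients whose clinical status changes after randomization so that they no longer qualify. It expects some screen failures because the plan changes to ED discharge. It does not say whether patients so labelled after randomization stay in the FAS.

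The plan does not define study intervention or randomization in error. It does not say who decides, when, or on what data.

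**The concern.** The exclusion has two conditions, and both must hold: the patient was randomized in error, and the patient received no study intervention. In a placebo-controlled drug trial the second condition works much the same way in both arms. Here the arms are two places of care, and planned admission is itself an inclusion criterion (section 5.1). Whether the second condition is met therefore depends on the assigned arm and on what staff do once they know it.

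The first condition is also open to judgment after allocation. Randomization may occur at any time in the ED stay (section 7.3.1), but one exclusion criterion is assessed at ED disposition, and another rests on the clinician's or investigator's opinion that the patient does not belong in an observation unit (section 5.2). Section 10.4.5 says there will be no adjudication committee.

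If patients removed from one arm differ in DAOOH from those who remain, and their counterparts in the other arm are kept, the arm means separate with no treatment effect. This would happen in the primary analysis.

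**Working it through.** **Step 1. Reproduce the plan's sample size.** Section 10.5 gives SD 3.9, a difference of 1 day, two-sided alpha 0.05 and power 80%.

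- Fixed design: n per arm = 2 × [3.9 × (1.960 + 0.842) / 1]² = 238.8, so 239.
- With one O'Brien-Fleming look at 50% and a final critical value of about 1.97 (my assumption), n = 240.2. The plan says 240.
- Attrition: 240 / 0.90 = 266.7, so 267 per arm and 534 in total, as stated.

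The plan's figures reproduce.

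**Step 2. Apply the rule to an ineligible patient.** Reading A counts each arm's own care as the intervention, so admission is the usual-care intervention. Reading B counts SSU care only.

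| Assigned arm | What happens | Reading A | Reading B |
|---|---|---|---|
| SSU | Reaches the SSU | Kept | Kept |
| SSU | Sent straight to a ward | Can be dropped | Dropped |
| Usual care | Admitted | Kept | Dropped |
| Usual care | Leaves the ED without admission | Dropped | Dropped |

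Under A, the default path for usual care keeps the patient, while diversion from the SSU can remove one. Under B, every misrandomized usual-care patient goes, but only the diverted SSU patients do.

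**Step 3. Size.** Suppose a share f of an arm is removed and those patients average d fewer DAOOH than the rest of that arm. The full-arm mean is the remaining patients' mean minus f × d, so removal raises the arm mean by f × d. The arm difference (SSU minus usual care) moves by

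shift = f(SSU) × d(SSU) − f(UC) × d(UC).

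The documents give no value for f or d. The table assumes removal from one arm only, 240 per arm before removal, and a normal approximation with critical value 1.96. The standard error is 3.9 × √(1/[240(1 − f)] + 1/240).

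| f | Patients removed | d (days) | Shift (days) | Two-sided type I error |
|---|---|---|---|---|
| 1% | 2.4 | 2 | 0.02 | 5.0% |
| 2% | 4.8 | 5 | 0.10 | 5.9% |
| 5% | 12 | 5 | 0.25 | 10.7% |
| 5% | 12 | 10 | 0.50 | 28% |

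Worked line for the last row: SE = 3.9 × √(1/228 + 1/240) = 0.361; 0.50 / 0.361 = 1.386; Φ(1.386 − 1.960) + Φ(−1.386 − 1.960) ≈ 0.283 + 0.0004 ≈ 0.28.

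If the removal falls on usual care instead, the sizes are the same and the sign changes. If d = 0 there is no bias, and losing 5% of one arm only lowers power from 80.2% to 79.2%.

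**Step 4. Without the exclusion.** With every randomized patient kept, f = 0 in both arms, so the shift from this rule is zero. The planned 240 per arm and 534 in total do not change.

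**The case against.** A reader might infer that ineligible patients leave the SSU arm only, so that the primary result is biased in favour of the SSU. The documents do not support that.

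- Removal is not confined to one arm. A misrandomized usual-care patient who is discharged from the ED, or withdraws before admission, also meets the test. A misrandomized SSU patient who reaches the unit does not.
- The direction is not fixed. Section 10.4.3.1 treats both arms as interventions. But section 2.3.1 contrasts protocolized SSU care with routine care, section 6.1 presents SSU management as what is being tested, and the cost-effectiveness text in 10.4.3 speaks of intervention and control groups. That wording fits Reading B, which reverses the imbalance.
- A literal reading of the word any could count either arm's care for a patient in either arm. An SSU patient sent to a ward would then be kept, and the rule would be close to neutral. The plan does not say this is meant.
- Not every eligibility criterion marks a sicker patient. Planned ED discharge, for example, does not.

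A reader might also infer that the note in 10.1.1 contradicts 10.3. It does not do so directly: it concerns worsening before the SSU, not randomization in error, and it closes one obvious route by which sick SSU patients could be lost. What is missing is an order of precedence. An SSU patient who deteriorates in the ED could be described under 10.1.1, under the screen-failure text in 5.3, or as misrandomized under 10.3.

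The number affected may be small. Eligibility is confirmed at randomization (section 7.3.2), and exceptions to entry criteria are barred (sections 12 and 14.3). The 28% case needs 12 of 240 patients removed from one arm who average 10 days worse, about 2.6 SD (10 / 3.9), and nothing in the documents suggests that rate.

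These points limit the claim about direction and size. They do not remove the defect: the set called all randomized patients is not that, and the exception rests on an undefined term applied after an unblinded allocation.

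**Conclusion.** The point holds as a defect in the definition of the primary analysis set. The exclusion departs from the intention-to-treat statement beside it, depends on care after a known allocation, and can act unequally between arms under either reading in the working. It can therefore bias the primary DAOOH comparison. The documents do not show that it will, or which way.

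On assumed values, the shift runs from 0.02 day (type I error 5.0%) to 0.50 day (about 28%), against a target of 1 day. The range rests on three assumptions: the share removed (1% to 5%), the DAOOH difference of those removed (2 to 10 days), and removal from one arm with counterparts kept in the other. The lower end is negligible and the upper end would be serious. Since the correction costs almost nothing, it should be made without waiting to learn which applies.

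**What to change.** 1. Delete the sentence excluding misrandomized patients from sections 5.4.2 and 10.3, so that the FAS is every randomized patient in the assigned arm. Leave eligibility violators to the Per Protocol Set, which already excludes major protocol violations.
2. If some exclusion is kept, drop the condition on intervention received. Base the exclusion only on eligibility facts recorded before randomization, judged by someone blind to arm and outcome, and report a sensitivity analysis of all randomized patients.
3. State that patients labelled screen failures after randomization (section 5.3), and SSU patients who worsen before reaching the unit (section 10.1.1), stay in the FAS, so that these sections agree with 10.3.

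The cost is one sentence deleted in two places and one clarifying statement. Sample size is unchanged. A few ineligible patients remain in the primary analysis and may dilute the effect slightly.

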10.4 DESCRIPTION OF STATISTICAL METHODS

10.4.1 GENERAL APPROACH

Unless stated otherwise, two-sided p values < 0.05 will be considered statistically significant, without regard to multiple comparisons. Statistical tables and listings and analyses will be produced using SAS® release 9.1 or later (SAS Institute, Inc, Cary, NC, USA) or other validated statistical software.

10.4.2 ANALYSIS OF THE PRIMARY EFFICACY ENDPOINT(S)

Patient baseline characteristics will be tabulated for both SSU and usual care groups. Specifically, means (standard deviations) or medians (interquartile range) will be presented for continuous variables such as age and body mass index. For categorical variables, such as gender and race, frequency and percentages will be presented. Group comparisons of continuous variables will be based on either two-sample t-tests (under normality) or Wilcoxon's Rank Sum test. Normality of distribution will be determined using the Kolmogorov-Smirnov goodness-of-fit test. Categorical data comparisons will be presented based on the Chi-square or Fisher's exact test. Standardized difference is used to compare the mean of the SSU and usual care groups.⁷²

In-hospital and SSU measurements: Data points collected during hospitalization and the SSU (e.g. medications, therapy, changes in renal function, and discharge medications) will be compared between the SSU and usual care groups using the same methods as for baseline variables. A two-sided p -value less or equal to 0.05 is considered statistically significant (without multiplicity adjustment).

Comparison on DAOOH (primary outcome): The DAOOH will be compared between the two arms using two-sample t-test. Statistical significance will be declared at 5% level (two-sided). We will also fit a linear regression model, which includes the intervention arm indicator and the site variable (e.g. a categorical variable with four levels) as the covariates. The regression model will account for variation among sites so that the power in detecting intervention effect can be improved. It will also allow us to assess potential heterogeneity in intervention effect among sites through testing the interaction between the two covariates.

Capture of DAOOH Endpoint: Each study site uses an electronic health record with time stamps for ED arrival, time leaving the ED, time of arrival to SSU or inpatient admission, and time of discharge. Thus, exact times, rounded to the nearest hour, will be calculated to determine length of stay. Any time spent in the ED, SSU, or inpatient admission will count against their DAOOH. Although the endpoint uses the term "hospital," for the purposes of this analysis and its patient-centered focus, any time in these three hospital settings (ED, SSU, inpatient admission) will be counted. If a patient returns to the hospital or to the ER, the time spent (in hours) will be added to their total length of stay. This time does not need to be consecutive.

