Intervention Monitoring: To ensure fidelity of each component of the intervention between study arms, we will also measure the following individual components of the intervention throughout the trial at both the site and overall study level: 1) Baseline patient characteristics, 2) Medicine reconciliation 3) Guideline-HF adherence 4) SSU AHF protocol adherence, 5) admission rates from the SSU 6) Quality of Life/Caregiver Burden Questionnaire response and completeness, 7) Hospitalized patients discharged within 48 hours, and 8) Follow up completed at 30 days. These analyses will be reported every 3 months to the Steering Committee to allow for course correction as needed. In addition, these will be reported at the conclusion of the study as well as at quarterly enrollment milestones to the DSMB.

Sensitivity Analyses: Some baseline covariates such as co-morbidities, medications, renal function, serum sodium, potassium, b-type natriuretic peptide (BNP) or NT-pro BNP, and blood pressure, may not be well-balanced between the two arms despite randomization. These covariates are known markers of risk in AHF patients and are part of the standard assessment for the vast majority of AHF admissions. We will use the inverse probability weighting approach to adjust those covariates with poor balance between the arms as part of a sensitivity analysis.⁷⁵ We will then compare these results with those from the two-sample t test. In addition, if the DAOOH, QoL, caregiver burden, or mRUQ-HF endpoints are found to be non-normal in distribution, the Wilcoxon Rank-Sum test will be used for comparison as a sensitivity analysis.

Modified Resource Utilization Questionnaire for Heart Failure (mRUQ-HF).⁷⁰ The mRUQ-HF is a 14-item self-report questionnaire of comprehensive lists of choice related to healthcare utilization. (See Appendix trial protocol) Exploratory analysis will occur in two steps: 1) Determination of resources consumed or related; 2) Assignment of 'value' to the resources consumed.⁷¹ This two-step process allows for transparency of assigned costs. Hospital costs will be assigned per individual hospital cost-accounting. Where monetary values are not directly self-reported, Medicare fee schedules will be used for uniformity. This will be captured at 90 days and will include the hospitalization when patients answer the questionnaire.

All Cause Mortality and All-Cause Rehospitalization Endpoints:

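### The primary DAOOH test ignores the site stratification and the known risk markers; making the planned site-adjusted regression primary would recover some power at almost no cost

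*Combined protocol and SAP*

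**What the plan says.** Section 10.4.2 sets the primary comparison: "The DAOOH will be compared between the two arms using two-sample t-test". The next sentence gives the two-sided 5% significance rule. The section then continues: "We will also fit a linear regression model, which includes the intervention arm indicator and the site variable". It gives the reason: "The regression model will account for variation among sites so that the power in detecting intervention effect can be improved". It also plans a test of the arm-by-site interaction.

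Section 10.6.1 states the design: "Patients will be randomized 1:1 to one of the two study arms, but stratified by site to ensure equal site representation", with "random block sizes of two, four, and six will be created, stratified by site".

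Section 10.4.3.1 (Sensitivity Analyses) lists co-morbidities, medications, renal function, sodium, potassium, BNP or NT-proBNP, and blood pressure, and describes them as recognized risk markers. Their only planned use for the primary endpoint is this: "We will use the inverse probability weighting approach to adjust those covariates with poor balance between the arms as part of a sensitivity analysis". Those results are then compared with the t-test. No cutoff for poor balance is given.

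Elsewhere the plan does respect the hospital structure. The exploratory time-to-event composite in 10.4.3.1 uses a stratified log-rank test, and the cost-effectiveness models in 10.4.3 include hospital fixed effects. KCCQ is to be compared by the same method as the primary endpoint, so the choice made in 10.4.2 carries over to a secondary endpoint.

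**The concern.** Stratified blocks force near-equal numbers per arm within each site, so differences between sites contribute almost nothing to the actual variance of the difference in means. The two-sample t-test still counts those differences in its standard error. To the extent that site predicts DAOOH, the standard error is too large and the test is slightly conservative. The plan already contains the model that corrects this, but a model that does not decide significance cannot raise the power of the primary test.

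The baseline risk markers raise a separate issue. Adjusting only for those that turn out imbalanced selects covariates after seeing the data, and by chance imbalance rather than by how strongly they predict DAOOH. What is at stake is power in a trial planned at exactly 80%.

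**Working it through.** **Inputs from 10.5, 10.4.2 and 10.6.1.** Difference 1 day; SD 3.9; two-sided alpha 0.05; 240 evaluable per arm; 10% attrition; 1:1 allocation stratified by four sites.

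**Input not in the documents.** R², the share of DAOOH variance explained by site or by baseline covariates. A range is assumed below.

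**1. The plan's own figure.**
- Normal approximation: n per arm = 2 × (1.960 + 0.842)² × 3.9² / 1² = 238.8, so 239.
- The exact t-test calculation gives 239.7, so 240.
- With one O'Brien-Fleming-type look at half the information, 240.8 per arm is needed, and power at 240 is 79.9%.
- Attrition: 240 / 0.90 = 266.7, so 267 per arm and 534 in total.

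The stated sample size reproduces from the unadjusted SD.

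**2. Site omitted after stratification.** The t-test uses SE = 3.9 × √(2/240) = 0.356. Under stratified allocation the difference in means actually varies with SE × √(1 − R²). Hence:
- true size of the t-test = 2 × [1 − Φ(1.96 / √(1 − R²))]
- power of the t-test = Φ[(1 − 1.96 × 0.356) / (0.356 × √(1 − R²))]
- power of the site-adjusted test = Φ[1 / (0.356 × √(1 − R²)) − 1.96]

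| Assumed site R² | Residual SD | t-test true size | t-test power | Site-adjusted power | Loss (points) |
|---|---|---|---|---|---|
| 0 | 3.900 | 0.050 | 80.2% | 80.2% | 0 |
| 0.02 | 3.861 | 0.048 | 80.4% | 81.0% | about 0.5 |
| 0.05 | 3.801 | 0.044 | 80.8% | 82.2% | about 1.4 |
| 0.10 | 3.700 | 0.039 | 81.5% | 84.2% | about 2.7 |

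These are fixed-design normal approximations; losses are taken before rounding. Stratification raises the t-test's own power slightly, so the correct comparison is within a row and not against 80%.

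**3. Unstratified baseline covariates omitted.** Chance imbalance in these covariates is real variation that the t-test's standard error correctly includes. Its size therefore stays at 0.05 and its power at about 80%. Adjusted power with SD = 3.9 × √(1 − R²) at 240 per arm:
- R² 0.05: 82.2% (82.0% by the noncentral t)
- R² 0.10: 84.2% (84.0%)
- R² 0.20: 88.1%

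For scale, 267 evaluable per arm without adjustment gives about 84%, the same as 240 per arm with R² of 0.10.

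**4. Simulation.** Four equal sites, blocks of 2, 4 and 6, 480 analysed, 2,500 runs per scenario.
- Site R² 0.10: t-test size 0.032 and power 0.819, against site-adjusted power 0.845.
- Covariate R² 0.20: t-test size 0.049 and power 0.812, against covariate-adjusted power 0.881.

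The Monte Carlo standard error of a size near 0.05 is √(0.05 × 0.95 / 2,500) = 0.0044. The runs therefore support the power gains at the larger R² values, but cannot resolve the small size differences at site R² of 0.02–0.05. Those rest on the formula.

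**The case against.** The strongest reply is that nothing is broken. The t-test is valid and delivers the planned 80% power. Site adjustment is already pre-specified with its rationale, so the change only swaps which of two planned analyses is primary. The gain depends wholly on an R² that the documents do not give, and for site alone it may be about one power point. All of this stands, and it limits the weight of the point. It does not remove it, because the change is nearly free and the plan states the power argument itself.

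Three stronger readings are tempting, and the documents do not support them.
- A reader might infer that the plan leaves open whether the t-test or the regression decides. The 5% rule directly follows the t-test sentence, the regression is an addition, the sensitivity analyses use the t-test as their reference, and the sample size reproduces from it. The t-test governs.
- A reader might infer that leaving out baseline covariates also makes the test conservative. Only the omitted stratification factor does that.
- A reader might infer that every listed marker is available for every patient. Sections 7.2.1, 7.3.1 and 7.3.7 tie laboratory tests to usual care, BNP or NT-proBNP follows local practice, and 10.4.3.1 speaks only of most admissions. A complete-case model that required natriuretic peptide could drop patients from the Full Analysis Set and erode the gain.

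**Conclusion.** The point holds as a modest efficiency loss. The primary decision rests on an unadjusted test although the design stratifies by site. The planned site-adjusted model is secondary to it, and risk markers are used only when imbalanced.

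The loss from omitting site is about 0.5–1.4 power points at an assumed site R² of 0.02–0.05. The gain from adding covariates is about 2 points at an assumed R² of 0.05 and about 4 points at 0.10. These two figures should not be added as though independent, because some of the explained variance may be shared. If site and covariates explain nothing, nothing is lost. The result gives no ground for calling the sample size wrong, the estimate biased or the type I error inflated.

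**What to change.** In 10.4.2:
- Name the linear regression of DAOOH on arm and site, without interaction and with robust standard errors, as the primary analysis, and test the arm coefficient at the two-sided 5% level.
- Keep the t-test as supportive and the arm-by-site interaction as a separate assessment.
- Add a short covariate list, fixed before any comparative data are seen and used regardless of observed balance. Limit it to values available for essentially all patients, for example age, systolic blood pressure and renal function, all of which appear in the eligibility criteria. Age is not among the markers listed in 10.4.3.1 and would have to be added by name.
- Include natriuretic peptide only with a stated rule for missing baseline values and for BNP versus NT-proBNP, so that no Full Analysis Set patient is dropped. The multiple imputation in 10.4.5 is a possible starting point.

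In 10.4.3.1, base the inverse probability weighting on the same fixed list instead of on observed imbalance.

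The cost is an amendment to the analysis text, slightly more analysis work and a missing-covariate rule. No extra patients or assessments are needed.
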